12.5.2 Overall Best Response Assessment

Each patient will be classified according to his “best response” for the purposes of analysis of treatment effect. Best response is determined from the sequence of the overall response assessments as described in [Section 12.6](#).

12.6 Best Response

12.6.1 Evaluation of Best Overall Response

The best overall response is the best response recorded from the start of the

THIS PROTOCOL IS FOR RESEARCH PURPOSES ONLY, SEE PAGE 1 FOR USAGE POLICY

treatment until disease progression/recurrence (taking as reference for progressive disease the smallest measurements recorded since the treatment started). The patient's best response assignment will depend on the achievement of both measurement and confirmation criteria.

Table 3. Sequences of overall response assessments with corresponding best response.

1 st Assessment	2 nd Assessment	Best Response
Progression		Progressive disease
Stable, PR, CR	Progression	Progressive disease
Stable	Stable	Stable
Stable	PR, CR	Stable
Stable	Not done	Not RECIST classifiable
PR	PR	PR
PR	CR	PR
PR, CR	Not done	Not RECIST classifiable
CR	CR	CR

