12.2.5 Overall Response Assessment

Table 1: For Patients with Measurable Disease (i.e., Target Disease)

Target Lesions	Non-Target Lesions	New Lesions	Overall Response	Best Overall Response when Confirmation is Required*
CR	CR	No	CR	≥ 28 days Confirmation
CR	Non-CR/Non-PD	No	PR	≥ 28 days Confirmation
CR	Not evaluated	No	PR	
PR	Non-CR/Non-PD/not evaluated	No	PR	
SD	Non-CR/Non-PD/not evaluated	No	SD	documented at least once ≥ 28 days from baseline
PD	Any	Yes or No	PD	

THIS PROTOCOL IS FOR RESEARCH PURPOSES ONLY, SEE PAGE 1 FOR USAGE POLICY

Any	PD**	Yes or No	PD	no prior SD, PR or CR
Any	Any	Yes	PD	

* See RECIST 1.1 manuscript for further details on what is evidence of a new lesion. ** In exceptional circumstances, unequivocal progression in non-target lesions may be accepted as disease progression. Note: Patients with a global deterioration of health status requiring discontinuation of treatment without objective evidence of disease progression at that time should be reported as “symptomatic deterioration.” Every effort should be made to document the objective progression even after discontinuation of treatment.
				

Table 2: For Patients with Non-Measurable Disease (i.e., Non-Target Disease)

Non-Target Lesions	New Lesions	Overall Response
CR	No	CR
Non-CR/non-PD	No	Non-CR/non-PD*
Not all evaluated	No	not evaluated
Unequivocal PD	Yes or No	PD
Any	Yes	PD

* ‘Non-CR/non-PD’ is preferred over ‘stable disease’ for non-target disease since SD is increasingly used as an endpoint for assessment of efficacy in some trials so to assign this category when no lesions can be measured is not advised
		

Table 4: Overall Response for Patients with Neuroblastoma and Measurable Disease

CT/MRI	MIBG	Bone Scan	Bone Marrow	Catechol	Overall
PD	Any	Any	Any	Any	PD
Any	PD	Any	Any	Any	PD
Any	Any	PD	Any	Any	PD
Any	Any	Any	PD	Any	PD
SD	CR/PR/SD	Non-PD	Non-PD	Any	SD
PR	CR/PR	Non-PD	Non-PD	Any	PR
CR/PR	PR	Non-PD	Non-PD	Any	PR
CR	CR	Non-PD	Non-PD	Elevated	PR
CR	CR	CR	CR	Normal	CR

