12.6.2 Duration of Response

12.6.2.1 Duration of overall response: The duration of overall response is measured from the time measurement criteria are met for CR or PR (whichever is first recorded) until the first date that recurrent or progressive disease is objectively documented (taking as reference for progressive disease the smallest measurements recorded since the treatment started).

The duration of overall CR is measured from the time measurement criteria are first met for CR until the first date that progressive disease is objectively documented.

12.6.2.2 Duration of stable disease: Stable disease is measured from the start of the treatment until the criteria for progression are met, taking as reference the smallest measurements recorded since the treatment started, including the baseline measurements.

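### Two rows of Table 3 (12.6.1) contradict the protocol's other best-response rules for measurable disease and under-report stable disease; the Part B go/no-go counts are not affected

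*Combined protocol and SAP*

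**What the plan says.** **Section 12.6.1, text.** The opening sentence reads "The best overall response is the best response recorded from the start of the" treatment, and continues up to progression or recurrence. The next sentence adds that the "best response assignment will depend on the achievement of both measurement and confirmation criteria".

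**Section 12.6.1, Table 3.** The caption is "Sequences of overall response assessments with corresponding best response". Two rows matter here:
- Stable, PR or CR at the first assessment and progression at the second gives progressive disease.
- Stable at the first assessment and no second assessment gives "Not RECIST classifiable". PR or CR with no second assessment gets the same label.

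**Section 12.2.5, Table 1 (measurable disease).** The last column states what best overall response needs when confirmation is required. The CR row and the first PR row carry "≥ 28 days Confirmation". SD must be "documented at least once ≥ 28 days from baseline". PD carries "no prior SD, PR or CR". In the text available, the PD entry stands beside the row for progression in non-target lesions, and the cells of the other PD rows are empty.

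**Section 12.6.2.2.** "Stable disease is measured from the start of the treatment until the criteria for progression are met".

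**Use of these rules.** Section 12.2.6 sends best response, as part of the analysis of treatment effect, to section 12.6. Section 11.7 sends Part B response to section 12.0 in general. The Part B counts have their own definitions: response in 11.6, 11.7 and 12.2.1(a), and disease control in 11.6 and 11.7.

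**The concern.** Take a Part B patient with measurable disease who is stable at the first scan and has progressed at the second. The opening sentence of 12.6.1 and the SD row of Table 1 give a best response of stable disease. Table 3 gives progressive disease. A patient who is stable at the first scan and has no second one is stable by Table 1 and unclassified by Table 3.

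Two analysts who each follow a written rule would therefore report different best-response distributions from the same data. Table 3 is the likelier one to be programmed, because it looks like the working algorithm. It moves patients out of the stable category, into progression or into no category at all.

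**Working it through.** The contradiction is one of classification and rests on no figure. Arithmetic is needed only for scan timing and to check the scope.

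**1. Scan timing.** Cycles last 28 days (5.1), and Part B scans follow cycles 2, 4 and 6 (8.1). The first falls at about 2 × 28 = Day 56 and the second at about 4 × 28 = Day 112. Since 56 > 28, one stable reading at the first Part B scan already meets the SD condition of Table 1. Even if the scan is done 72 hours early, as 8.1 allows, 56 − 3 = 53 > 28.

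**2. The rows side by side** (measurable disease, first scan at about Day 56):

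| First / second assessment | Table 3 | 12.6.1 opening sentence with Table 1 |
|---|---|---|
| Progression / – | Progressive disease | Progressive disease (agrees) |
| Stable / Progression | Progressive disease | Stable |
| PR or CR / Progression | Progressive disease | Not progressive disease; not PR or CR either, as unconfirmed; Stable |
| Stable / Not done | Not classifiable | Stable |

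For PR or CR then progression, Stable is an inference: the patient was at least stable 28 days or more from baseline, and Table 3 itself records Stable then PR or CR as Stable.

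**3. Is the Part B decision touched?** The design table in 11.6 can be rebuilt from the response (R) and disease control (S) counts alone. With Pr(S|R) = 0.90, each patient falls in one of four cells:
- both: 0.90 × P(R)
- R only: 0.10 × P(R)
- S only: P(S) − 0.90 × P(R)
- neither: the remainder

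At P(S) = 0.20 and P(R) = 0.05 these are 0.045, 0.005, 0.155 and 0.795. The exact joint distribution is summed over 19 and then 10 patients. The trial stops at stage 1 if S ≤ 4 and R ≤ 1, and the drug is judged effective at the end if S ≥ 9 or R ≥ 5.

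| P(S), P(R) | Stop at stage 1: plan / recomputed | Effective: plan / recomputed |
|---|---|---|
| 0.20, 0.05 | 0.56 / 0.5639 | 0.11 / 0.1084 |
| 0.42, 0.22 | 0.014 / 0.0135 | 0.95 / 0.9492 |
| 0.42, 0.05 | 0.044 / 0.0448 | 0.904 / 0.9039 |
| 0.20, 0.22 | 0.056 / 0.0566 | 0.79 / 0.7887 |

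All agree to within 0.004, and best response from Table 3 enters nowhere. Patient by patient:
- *Disease control.* Section 11.7 judges status at four months or the end of cycle 6, whichever is first. A patient who has progressed by then is not a success. One lost after cycle 2 is also not a success. Neither result depends on Table 3.
- *Response.* Section 12.2.1(a) requires a centrally confirmed CR or PR before other anti-cancer therapy. Correcting the two rows turns progressive or unclassified patients into stable ones and creates no responder.

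**4. A separate conflict found on the way.** Consider a patient with a first PR who receives non-protocol anti-cancer therapy before confirmation and before progression. Section 11.7 makes this patient inevaluable for response. Section 12.2.1(a) makes anyone eligible with one dose evaluable, and a non-responder if not confirmed before such therapy. With one such patient among the 19 in stage 1, and no replacement, the response denominator is 19 under 12.2.1(a) and 19 − 1 = 18 under 11.7.

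**The case against.** The best defence of Table 3 is that it applies one consistent rule: nothing better than progression is credited on a single assessment. Stable twice is Stable, PR twice is PR, and anything followed by no scan is unclassified. The confirmation sentence of 12.6.1 supports that reading.

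Part of this stands. The Stable / Not done row does not contradict the text of 12.6.1, only Table 1. The documents also do not say which table governs. The defence is weaker for the progression row. Needing confirmation before PR is credited does not make a patient with a qualifying stable scan progressive. The criterion that Table 1 sets for SD, in a column about required confirmation, is one documentation.

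Two further objections stand:
- Section 12.6.2.2 says how to time stable disease, not who receives it as best response. It is supporting context and not a conflict.
- The PD entry in Table 1 can be seen beside one PD row only. Whether it spans the others cannot be verified. The conflict with the opening sentence of 12.6.1 does not need it.

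A reader might infer a stronger point in two ways, and the documents support neither:
- *That Table 3 distorts the go/no-go decision or costs power.* This would require response or disease control to be scored from Table 3, which 11.6, 11.7 and 12.2.1(a) do not do.
- *That the number of misclassified patients can be calculated,* by subtracting the null P(S) of 0.20 from the 45.2% of adults with stable disease for 8 weeks or more (2.3.1). These are unlike quantities. The adult share counts stable disease only, in mixed tumors, while P(S) includes CR and PR. Patients who fail disease control also include those lost to follow-up, who need not have progressed. The difference is neither an estimate nor an upper limit.

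**Conclusion.** Wrong as written, and minor. For measurable disease, the row for SD, PR or CR then progression contradicts the opening sentence of 12.6.1 and the PD entry of Table 1, subject to the layout limit on that entry. The row for SD then no assessment contradicts Table 1. The direction is clear: stable disease is under-reported as best response. The documents support no numerical size.

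The Part B decision is unaffected, and other response reporting is descriptive (11.5). These conclusions rest on two assumptions: that the Part B counts are scored from their own definitions, and that an unconfirmed PR or CR is not credited as response.

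The conflict between 11.7 and 12.2.1(a) is real but independent of Table 3. Unlike the two rows, it can change the Part B response denominator.

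**What to change.** 1. **Table 3, measurable disease.** Make it agree with Table 1. Stable, PR or CR followed by progression is best response Stable if at least SD was documented 28 days or more from baseline, and otherwise progressive disease. Stable, PR or CR followed by no assessment is Stable on the same condition, and otherwise not classifiable. State that an unconfirmed PR or CR is not a response. Label the rule as being for measurable disease, because sections 12.3.6, 12.4.5 and 12.5.2 send other patients to 12.6 and Table 1 does not cover them.
2. **12.6.1.** State that the best result over successive assessments up to progression is kept.
3. **11.7.** State that Table 3 does not score the Part B response or disease control counts. This closes the gap left by the general reference to section 12.0 without adding a new responder rule.
4. **Separately, 11.7 and 12.2.1(a).** Choose one rule, inevaluable or non-responder, for patients given non-protocol anti-cancer therapy after a first PR or CR and before confirmation, and use it in both places.

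The cost is text edits only, in 12.6.1, 11.7 and possibly 12.2.1(a). No scans, patients or changes to the decision thresholds are needed.

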12.6.2 Duration of Response

12.6.2.1 Duration of overall response: The duration of overall response is measured from the time measurement criteria are met for CR or PR (whichever is first recorded) until the first date that recurrent or progressive disease is objectively documented (taking as reference for progressive disease the smallest measurements recorded since the treatment started).

The duration of overall CR is measured from the time measurement criteria are first met for CR until the first date that progressive disease is objectively documented.

12.6.2.2 Duration of stable disease: Stable disease is measured from the start of the treatment until the criteria for progression are met, taking as reference the smallest measurements recorded since the treatment started, including the baseline measurements.

13.0 ADVERSE EVENT REPORTING REQUIREMENTS

Adverse event data collection and reporting which are required as part of every clinical trial, are done to ensure the safety of patients enrolled in the studies as well as those who will enroll in future studies using similar agents. Adverse events are reported in a routine manner at scheduled times during a trial. (Please follow directions for routine reporting provided in the Case Report Forms for this protocol). Additionally, certain adverse events must be reported in an expedited manner to allow for optimal monitoring of patient safety and care. The following sections provide information about expedited reporting.

Reporting requirements may include the following considerations: 1) whether the patient has received an investigational or commercial agent; 2) whether the adverse event is considered serious; 3) the grade (severity); and 4) whether or not hospitalization or prolongation of hospitalization was

associated with the event.

An investigational agent is a protocol drug administered under an Investigational New Drug Application (IND). In some instances, the investigational agent may be available commercially, but is actually being tested for indications not included in the approved package label.

Commercial agents are those agents not provided under an IND but obtained instead from a commercial source. The NCI, rather than a commercial distributor, may on some occasions distribute commercial agents for a trial.

13.1 Steps to Determine If an Adverse Event Is To Be Reported In an Expedited Manner

Step 1: Identify the type of adverse event using the NCI CTCAE version 5.0. All appropriate treatment areas should have access to a copy of the CTCAE version 5.0. A copy of the CTCAE version 5.0 can be downloaded from the CTEP website (http://ctep.cancer.gov/protocolDevelopment/electronic_applications/ctc.htm).

Step 2: Grade the adverse event using the NCI CTCAE.

Step 3: Review Table A in this section to determine if:

- the adverse event is considered serious;
- there are any protocol-specific requirements for expedited reporting of specific adverse events that require special monitoring; and/or
- there are any protocol-specific exceptions to the reporting requirements.

Note: This includes all events that occur within 30 days of the last dose of protocol treatment. Any event that occurs more than 30 days after the last dose of treatment and is attributed (possibly, probably, or definitely) to the agent(s) must also be reported according to the instructions in the table below. Attribution categories are as follows: Unrelated, Unlikely, Possible, Probable, and Definite.

Table A: Phase 1 and Early Phase 2 Studies: Expedited Reporting Requirements for Adverse Events that Occur on Studies under an IND/IDE within 30 Days of the Last Administration of the Investigational Agent/Intervention^{1,2}

FDA REPORTING REQUIREMENTS FOR SERIOUS ADVERSE EVENTS (21 CFR Part 312)

NOTE: Investigators **MUST** immediately report to the sponsor **ANY** Serious Adverse Events, whether or not they are considered related to the investigational agent(s)/intervention (21 CFR 312.64)

An adverse event is considered serious if it results in **ANY** of the following outcomes:

- 1) Death
- 2) A life-threatening adverse event
- 3) An adverse event that results in inpatient hospitalization or prolongation of existing hospitalization for \geq 24 hours
- 4) A persistent or significant incapacity or substantial disruption of the ability to conduct normal life functions
- 5) A congenital anomaly/birth defect.
- 6) Important Medical Events (IME) that may not result in death, be life threatening, or require hospitalization may be considered serious when, based upon medical judgment, they may jeopardize the patient or subject and may require medical or surgical intervention to prevent one of the outcomes listed in this definition. (FDA, 21 CFR 312.32; ICH E2A and ICH E6).

THIS PROTOCOL IS FOR RESEARCH PURPOSES ONLY, SEE PAGE 1 FOR USAGE POLICY

ALL SERIOUS adverse events that meet the above criteria MUST be immediately reported via CTEP-AERS within the timeframes detailed in the table below.		
Hospitalization	Grade 1 and Grade 2 Timeframes	Grade 3-5 Timeframes
Resulting in Hospitalization ≥ 24 hrs	7 Calendar Days	24-Hour 5 Calendar Days
Not resulting in Hospitalization ≥ 24 hrs	Not required	

NOTE: Protocol specific exceptions to expedited reporting of serious adverse events are found in the Specific Protocol Exceptions to Expedited Reporting (SPEER) portion of the CAEPR.
 
Expedited AE reporting timelines are defined as:
 
 ○ “24-Hour; 5 Calendar Days” - The AE must initially be reported via CTEP-AERS within 24 hours of learning of the AE, followed by a complete expedited report within 5 calendar days of the initial 24-hour report. ○ “7 Calendar Days” - A complete expedited report on the AE must be submitted within 7 calendar days of learning of the AE. 
¹Serious adverse events that occur more than 30 days after the last administration of investigational agent/intervention and have an attribution of possible, probable, or definite require reporting as follows: Expedited 24-hour notification followed by complete report within 5 calendar days for:
 
 • All Grade 3, 4, and Grade 5 AEs 
Expedited 7 calendar day reports for:
 
 • Grade 2 AEs resulting in hospitalization or prolongation of hospitalization 
² For studies using PET or SPECT IND agents, the AE reporting period is limited to 10 radioactive half-lives, rounded UP to the nearest whole day, after the agent/intervention was last administered. Footnote “1” above applies after this reporting period.
 
Effective Date: May 5, 2011
		

- Any medical event equivalent to CTCAE grade 3, 4, or 5 that precipitates hospitalization (or prolongation of existing hospitalization) must be reported regardless of attribution and designation as expected or unexpected with the exception of any events identified as protocol-specific expedited adverse event reporting exclusions.
- Any event that results in persistent or significant disabilities/incapacities, congenital anomalies, or birth defects must be reported via CTEP-AERS if the event occurs following treatment with an agent under a CTEP IND.
- Use the NCI protocol number and the protocol-specific patient ID provided during trial registration on all reports.

Additional Instructions or Exceptions to CTEP-AERS Expedited Reporting Requirements for Phase 1 Trials Utilizing an Agent under a CTEP-IND or Non-CTEP IND:

- Any death that occurs more than 30 days after the last dose of treatment with an investigational agent which can be attributed (possibly, probably, or definitely) to the agent and is not clearly due to progressive disease must be reported via CTEP-AERS for an agent under a CTEP or non-CTEP IND agent per the timelines outlined in the table above.
- Myelosuppression, (Grade 1 through Grade 4 adverse events as defined in the table below), does not require expedited reporting, unless it is associated with hospitalization.

THIS PROTOCOL IS FOR RESEARCH PURPOSES ONLY, SEE PAGE 1 FOR USAGE POLICY

Category	Adverse Events
INVESTIGATIONS	Platelet count decreased
INVESTIGATIONS	White blood cell decreased
INVESTIGATIONS	Neutrophil count decreased
INVESTIGATIONS	Lymphocyte count decreased
BLOOD/LYMPHATICS DISORDERS	Anemia

- Grade 1 and 2 adverse events listed in the table below do not require expedited reporting via CTEPAERS, unless it is associated with hospitalization

Category	Adverse Events
GASTROINTESTINAL DISORDERS	Nausea
GENERAL DISORDERS AND ADMINISTRATION SITE CONDITIONS	Fatigue
MUSCULOSKELETAL AND CONNECTIVE TISSUE DISORDERS	Arthralgia
GASTROINTESTINAL DISORDERS	Decreased appetite
IMMUNE SYSTEM DISORDERS	Infusion-related reaction
INFECTIONS AND INFESTATIONS	Fever
MUSCULOSKELETAL AND CONNECTIVE TISSU DISORDERS	Myalgia
SKIN AND SUBCUTANEOUS DISORDERS	Pruritus

As referenced in the CTEP Adverse Events Reporting Requirements, an AE that resolves and then recurs during a subsequent cycle does not require CTEP-AERS reporting unless (1) the Grade increases; or (2) hospitalization is associated with the recurring AE.

13.2 When to Report an Event in an Expedited Manner

- Some adverse events require notification **within 24 hours** (refer to Table A to NCI via the web at <http://ctep.cancer.gov> (email the ADVL1614 COG assigned study Research Coordinator within 24 hours of becoming aware of the event if the CTEP-AERS 24-Hour Notification web-based application is unavailable) and by telephone call to the Study Chair. Once internet connectivity is restored, a 24-hour notification phoned in must be entered electronically into CTEP-AERS by the original submitter at the site.
- When the adverse event requires expedited reporting, submit the report **within 5 or 7 calendar days** of learning of the event (refer to Table A).
- Expedited AE reporting for this study must only use CTEP-AERS (Adverse Event Expedited Reporting System), accessed via the CTEP home page <https://eapps-ctep.nci.nih.gov/ctepaers>.

13.3 Expedited Reporting Methods

13.3.1 CTEP-AERS Reporting

To report adverse events in an expedited fashion use the NCI's Adverse Event Expedited Reporting System (CTEP-AERS) that can be found at <http://ctep.cancer.gov>.

A CTEP-AERS report must be submitted electronically via the CTEP-AERS Web-

THIS PROTOCOL IS FOR RESEARCH PURPOSES ONLY, SEE PAGE 1 FOR USAGE POLICY

based application located at <https://eapps-ctep.nci.nih.gov/ctepaers/>. If prompted to enter a sponsor email address, please type in: [contact].

Send supporting documentation by email to the ADV1614 COG study assigned Research Coordinator. **ALWAYS include the ticket number on all faxed and emailed documents.**

